4. STUDY REGISTRATION

The patient must willingly consent after being informed of the procedures to be followed, the experimental nature of the treatment, potential benefits, alternatives, side-effects, risks and discomforts. Human protection committee approval of this protocol and informed consent form are required.

CONFIDENTIAL

STUDY DRUG: Orteronel

SCRI INNOVATIONS STUDY NUMBER: BRE 203

DATE OF PROTOCOL: Version 3.0 30 October 2013

Patients will sign a pre-screen informed consent form (ICF) for centralized determination of AR expression in an archived tumor sample from a primary biopsy or metastatic lesion. Patients whose tumors have an AR expression $\geq 10\%$ will then sign and date the main ICF and will be screened to determine eligibility for enrollment into the study. Eligible patients who wish to participate in the study will be enrolled into the study. Patients with $\geq 10\%$ AR expression in their tumor tissue based on local lab assessment may enroll on the study, but will be required to provide tumor tissue for confirmation at the central laboratory.

Registration must occur prior to the initiation of protocol therapy. Patients eligible to participate in the study may be enrolled through the SCRI Innovations by calling [name]. Registration may be done via [contact] Monday through Friday, 8:30 a.m. to 4:30 p.m., Central Standard Time. Patient registration will be confirmed within 24 hours, or by the next business day.

5. STUDY DESIGN

This is an open-label, multicenter, Phase II study to be conducted in 2 stages. All patients will receive orteronel PO at a dose of 300 mg twice daily (BID) (600 mg total daily dose).

- Lead-in Phase: The first 6 patients treated will be evaluated every week to confirm the safety and feasibility of this regimen. After all 6 patients complete at least 4 weeks of treatment, and if no prohibitive toxicities are identified, continuous study treatment will begin.
- Continuous Study Treatment: Patients will continue to be enrolled into both cohorts based on their tumor specificities up to a total of 31 patients in Cohort 1 (ER-/PR-/HER2-/AR+) and 55 patients in Cohort 2 (ER+ and/or PR+/AR+). These numbers include the patients that are participating in the lead-in phase.

Up to 86 patients are planned to be enrolled in this study (6 for the lead-in phase and 80 for continuous study treatment).

Patients will be evaluated every eight weeks for response to treatment.

All patients who respond to treatment (complete response [CR] or partial response [PR]) or have stable disease (SD) will continue to receive orteronel until they develop progressive disease (PD) or unacceptable toxicity.

The study design schema is presented in Figure 1.

[figure not shown]
CONFIDENTIAL

STUDY DRUG: Orteronel

SCRI INNOVATIONS STUDY NUMBER: BRE 203

DATE OF PROTOCOL: Version 3.0 30 October 2013

Figure 1. BRE 203 Treatment Schema

5.1. Treatment Plan

All patients entering this study will receive continuous 300 mg orteronel PO BID as monotherapy. In the event of prohibitive toxicity, the orteronel dose may be reduced by one level to 200 mg BID.

5.2. Correlative Studies

The PI3Ks are a family of lipid kinases that regulate an intracellular signal transduction network, which in turn controls many features of cell behavior including growth, survival, motility, metabolism, and additional specialized functions. Several activating mutations in the PIK3CA gene encoding p110 alpha have been identified. In addition, the PI3K pathway is activated in

CONFIDENTIAL

STUDY DRUG: Orteronel

SCRI INNOVATIONS STUDY NUMBER: BRE 203

DATE OF PROTOCOL: Version 3.0 30 October 2013

cancers with mutations causing inactivation or silencing of the PTEN, a tumor suppressor gene. Breast cancers frequently harbor molecular/genomic aberrations that increase activation of the PI3K signaling pathway including loss of PTEN function or activating PIK3CA mutations (Engelman, 2009). Recent studies have found that AR is expressed in 60% to 70% of breast cancers regardless of ER status (Niemeier et al. 2010). Studies have also shown that there were significant differences in AR expression levels by PIK3CA mutation status (Gonzalez-Angulo et al. 2009). Interestingly, prostate cancer is characterized by its dependence on AR and frequent activation of PI3K signaling. A recent study has shown that these two oncogenic pathways cross-regulate each other by reciprocal feedback. Inhibition of one activates the other, thereby maintaining tumor cell survival (Carver et al. 2011). We proposed to test the PIK3CA mutation status and PTEN loss in patients in this study to investigate whether the activation of PI3K pathway correlates with the response to orteronel treatment.

PIK3CA mutation at codons 88, 539-549, 1020-1025, 1043-1049 will be tested by pyrosequencing and the results will be signed off by a molecular pathologist. PTEN loss will be determined by immunohistochemical staining using Ventana systems and the report will be signed off by a pathologist. Both assays will be performed at a CLIA/CAP certified lab. These analyses are exploratory, and will not be used to guide treatment decisions.

5.2.1. Blood samples for measuring serum hormone levels

Blood samples will be collected at baseline, on Cycle 2 Day 1, on Cycle 4 Day 1, and at the End-of-Treatment Visit to test for serum levels of estradiol, total and free testosterone, SHBG, ACTH, DHEA-S, and cortisol. A blood sample will be collected for this purpose from each patient at the noted time points (see Appendix E) and submitted to a laboratory for testing. Details of the laboratory will be provided to the site by the study team. When the results are received by the site, they will be entered into the appropriate eCRF page.

5.3. Concomitant Medications

Patients will be instructed not to take any additional medications during the course of the study without prior consultation with the research team. At each visit, the patient will be asked about any new medications he/she is taking or has taken after the start of the study drug.

5.3.1. Permitted Concomitant Medications

- Use of erythropoietin replacement or bisphosphonates or denosumab is considered supportive care, and their use is permitted, if initiated >2 weeks prior to study treatment.
- Patients are permitted to receive palliative radiation therapy on study to pre-existing, symptomatic lesions at the discretion of the treating physician.

All other drugs are allowed with the exception of those listed in Section 5.3.2.

CONFIDENTIAL

STUDY DRUG: Orteronel

SCRI INNOVATIONS STUDY NUMBER: BRE 203

DATE OF PROTOCOL: Version 3.0 30 October 2013

5.3.2. Prohibited Concomitant Medications

The following treatments are prohibited while in this study:

- Other investigational drug treatments or study participation
- Other treatment for breast cancer including hormonal therapy, chemotherapy, biologic therapy, immunotherapy, or radiation therapy (except as described in Section 5.3.1). Specific excluded hormonal therapies include estrogens, progestins, or herbal products. Patients with HER2+ tumors should have completed trastuzumab therapy.
- Concomitant treatment with any medication that may cause QT prolongation or Torsades de Pointes (see Appendix D). If a patient, after study enrollment, requires use of a medication that may cause QT prolongation and/or Torsades de Pointes that cannot be safely substituted, the patient must be removed from the study.
- Ketoconazole
- Aminoglutethimide
- Abiraterone (Zytiga®)
- Enzalutamide (MDV-3100)
- 5-alpha reductase inhibitors (eg, finasteride or dutasteride)
- Chronic systemic corticosteroids. If mineralocorticoid-related AEs occur and cannot be managed by supportive care (e.g., potassium, antihypertensives) and/or dose modification, low-dose corticosteroids (≤ 20 mg/day prednisone or its equivalent) can be given at the discretion of the investigator.
- Over-the-counter products such as vitamins, minerals, herbal preparations/medications and other dietary supplements are not allowed throughout the study; over-the-counter multivitamins without antioxidants are allowed. Patients should stop using these herbal medications at least 7 days prior to the first dose of study drug.

6. DOSE MODIFICATIONS

Toxicity will be assessed utilizing the NCI CTCAE v4.0 (<http://evs.nci.nih.gov/ftp1/CTCAE/CTCAE>), unless otherwise specified.

6.1. Dose Modifications and Reductions

Orteronel, at the dose used in this protocol, is expected to be well tolerated. Substantial acute toxicities should be managed as medically indicated and with temporary suspension of study drug, as appropriate. Dose reductions or holds and initiation of supportive care are allowed as clinically indicated by the treating physician. For each patient, a maximum of 1 dose reduction will be allowed. The reduced dose level is presented in Table 1. Should the patient not tolerate the lowest possible dose, he/she must discontinue treatment with orteronel.

CONFIDENTIAL

STUDY DRUG: Orteronel

SCRI INNOVATIONS STUDY NUMBER: BRE 203

DATE OF PROTOCOL: Version 3.0 30 October 2013

Table 1. Orteronel Dose Level Modifications

Dose Level	Orteronel BID/Daily
Starting Dose Level	0
Reduced Dose Level	-1

6.1.1. Criteria for Orteronel Dose Reduction

Sections 6.1.1.1 and 6.1.1.2 give management guidelines for treatment-related Grade 2, 3, and 4 toxicities. Subsequent sections present additional details regarding management of specific toxicities (Sections 6.1.3.1 through 6.1.3.8).

6.1.1.1. Grade 3 and 4 Toxicities

Dose modifications for acute renal insufficiency and abnormal liver function tests are presented separately in Sections 6.1.3.7 and 6.1.3.8, respectively.

Grade 4 non-hematologic toxicity: Discontinue orteronel

Grade 3 toxicities:

Grade 3 AEs that are considered at least possibly related to study drug require a dosing hold for a minimum of 2 weeks.

Once the dose is reduced, reassessment is required at least every 2 weeks until the event is resolved or stabilized. However, the frequency of reassessment should be increased as clinically indicated. If the grade worsens at any time, the dose should be decreased in accordance with the guidelines for the worst grade.

After the toxicity has improved to \leq Grade 1, orteronel should be restarted with a dose reduction. If the Grade 3 toxicity recurs on the reduced orteronel dose, the drug should be discontinued. Dose reduction for a Grade 3 toxicity is permanent; orteronel should not be re-escalated. Any patient who requires a treatment delay of more than 3 weeks due to treatment-related toxicity will be discontinued from study treatment, unless the treating physician and the Medical Monitor or Study Chair agree that continued treatment at lower doses is in the best interest of the patient.

Asymptomatic Grade 3 or 4 laboratory findings may not require dose modification (ie, dose hold or reduction) especially if these are not considered to be clinically significant or related to study drug. The decision to modify the dose should be based on the investigator's clinical judgment. Dose modifications for Grade 3 hyperglycemia should follow the guidelines in Table 6.

6.1.1.2. Grade 2 Clinically Intolerable Toxicities

Dose modifications for acute renal insufficiency and abnormal liver function tests are presented separately in Sections 6.1.3.7 and 6.1.3.8, respectively.

CONFIDENTIAL

STUDY DRUG: Orteronel

SCRI INNOVATIONS STUDY NUMBER: BRE 203

DATE OF PROTOCOL: Version 3.0 30 October 2013

For a clinically intolerable Grade 2 AE that is considered at least possibly related to study drug, the dose should be decreased by 1 dose level for 2 weeks. The investigator should identify other potential causes of any AE or laboratory abnormality, and consult with the Medical Monitor for any questions regarding the need for dose modification.

Once the dose is reduced, reassessment is required at least every 2 weeks until the event is resolved or stabilized. However, the frequency of reassessment should be increased as clinically indicated.

Subsequent dosing of orteronel should be based on the following guidelines:

- If the AE grade improves to Grade 0 or 1, re-escalate to the full dose (300 mg BID). If the intolerable Grade 2 toxicity recurs, the orteronel dose should be reduced permanently.
- If the AE remains at Grade 2 and is still intolerable after 2 weeks, hold administration of orteronel. If the AE grade improves to \leq Grade 1 within 3 weeks, and continued treatment is thought to be in the patient's best interest, orteronel may be restarted at the same (reduced) dose.
- If the event worsens to \geq Grade 3, hold orteronel for 2 weeks followed by a reassessment. If the AE grade improves to \leq Grade 1 within 3 weeks, and continued treatment is thought to be in the patient's best interest, orteronel may be restarted at the same (reduced) dose.

Reassess the AE after 2 weeks, or sooner, if the AE worsens. Continue to reassess at least every 2 weeks until the event is improved or stabilized. If the dose has been withheld for 3 weeks, orteronel will be discontinued permanently, unless the treating physician and the Medical Monitor or Study Chair agree that continued treatment at the minimum-allowed dose (200 mg BID) is in the best interest of the patient.

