6.1.3. Dose Modifications Due to Non-Hematologic Toxicity

Due to its mechanism of action, treatment with orteronel may elicit expression of adverse reactions typically associated with androgen deprivation. Risks associated with androgen deprivation include hot flushes, decreased libido, loss of energy, QTc interval prolongation, or mood swings. Long-term effects of testosterone suppression may also occur, including effects on bone mineral density, muscle mass, hyperglycemia, or lipid or energy metabolism.

Adverse events commonly recorded during clinical trials with orteronel include fatigue, nausea and vomiting, rash, and worsening hypertension. Pancreatitis and/or elevated amylase/lipase have also been reported, occurring in <5% of patients in studies conducted with orteronel.

CONFIDENTIAL

STUDY DRUG: Orteronel

SCRI INNOVATIONS STUDY NUMBER: BRE 203

DATE OF PROTOCOL: Version 3.0 30 October 2013

Pancreatic enzymes will be measured during scheduled serum chemistries for patients receiving long-term administration of orteronel.

For fatigue, mild or intermittent nausea and vomiting, or rash, dose modifications of orteronel should follow the guidelines in Section 6.1.1, depending on the severity.

For \geq Grade 3 QTc interval prolongation (QTcF >500 ms or >60 ms change from baseline on at least two separate ECGs), orteronel should be held until recovery to \leq Grade 1 (<480 ms). The patient's chemistries should be checked, as well as concomitant medication usage. Once QTc interval prolongation has resolved, orteronel may be restarted at the reduced dose level. For a second occurrence of \geq Grade 3 QTc interval prolongation, orteronel should be discontinued.

In the event of any grade 4 non-hematologic toxicity, orteronel should be discontinued.

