6.1.3.2. Gastrointestinal Adverse Events

Nausea

Nausea is defined as a disorder characterized by a queasy sensation and/or the urge to vomit. Table 3 summarizes the CTCAE Criteria (Version 4.0) for nausea and the appropriate actions to be followed.

CONFIDENTIAL

STUDY DRUG: Orteronel

SCRI INNOVATIONS STUDY NUMBER: BRE 203

DATE OF PROTOCOL: Version 3.0 30 October 2013

Table 3 **CTCAE Criteria and Appropriate Actions for Nausea**

CTCAE Grade	Event Definition	Action Required
1	Loss of appetite without alteration in eating habits	No action required
2	Oral intake decreased without significant weight loss, dehydration, or malnutrition	Concomitant anti-emetics may initially be administered without dose reduction. If Grade 2 nausea persists and is intolerable, dose reduction and re-escalation should follow Grade 2 Dose Reduction and Dose Re-escalation guidelines
3	Inadequate oral caloric or fluid intake; tube feeding, TPN, or hospitalization indicated	Supportive care regimen should follow local standard of care. Follow Dose Reduction and Dose Re-escalation guidelines

Source: NCI CTCAE Version 4.0

Abbreviation: CTCAE = Common Terminology Criteria for Adverse Events; TPN = total parenteral nutrition

Vomiting

Vomiting is defined as a disorder characterized by the reflexive act of ejecting the contents of the stomach through the mouth. Table 4 summarizes the CTCAE Criteria (Version 4.0) for vomiting and the appropriate actions to be followed.

Table 4 **CTCAE Criteria and Appropriate Actions for Vomiting**

CTCAE Grade	Event Definition	Action Required
1	Vomiting 1 to 2 episodes (separated by 5 minutes) in a 24-hour period	No action required
2	Vomiting 3 to 5 episodes (separated by 5 minutes) in a 24-hour period	Concomitant anti-emetics may initially be administered without dose reduction. If Grade 2 vomiting persists and is intolerable, dose reduction should follow Grade 2 Dose Reduction and Dose Re-escalation guidelines
3	Vomiting \geq 6 episodes (separated by 5 minutes) in a 24-hour period; tube feeding, TPN, or hospitalization indicated	Dose reduction follows Grade 3 Dose Reduction and Dose Re-escalation guidelines
4	Life-threatening consequences; urgent intervention indicated	Discontinue orteronel

Source: CTCAE Version 4.0

Abbreviation: CTCAE = Common Terminology Criteria for Adverse Events; TPN = total parenteral nutrition

CONFIDENTIAL

STUDY DRUG: Orteronel

SCRI INNOVATIONS STUDY NUMBER: BRE 203

DATE OF PROTOCOL: Version 3.0 30 October 2013

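### The worsening rule in Section 6.1.1.2 has no upper grade limit, so as written it permits a restart after Grade 4 toxicity for which Sections 6.1.1.1 and 6.1.3 require discontinuation

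*Combined protocol and SAP*

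**What the plan says.** Section 6.1.1.2 sets out what to do with a clinically intolerable Grade 2 event that is at least possibly related to orteronel. The dose goes down one level for 2 weeks, and three bullets then govern later dosing. The third bullet takes the case where the event gets worse. Its trigger is ≥ Grade 3, and its instruction is "Grade 3, hold orteronel for 2 weeks followed by a reassessment". If the event recovers to Grade 1 or lower within 3 weeks and continuing is judged to serve the patient, "orteronel may be restarted at the same (reduced) dose". Section 6.1 allows one reduction per patient, and Section 5.1 gives the reduced level as 200 mg BID, so that is the restart dose.

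Two general rules deal with Grade 4. Section 6.1.1.1 states "Grade 4 non-hematologic toxicity: Discontinue orteronel". Section 6.1.3 states "In the event of any grade 4 non-hematologic toxicity, orteronel should be discontinued". Section 6.1.1.1 also addresses worsening: "If the grade worsens at any time, the dose should be decreased in accordance with the guidelines for the worst grade". It leaves asymptomatic Grade 3 or 4 laboratory findings to the investigator's judgment.

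The event tables in Section 6.1.3 connect the two sets of rules. The Grade 2 rows of Tables 2, 7 and 9 name Section 6.1.1.2. Those of Tables 3, 4 and 5 refer to the Grade 2 dose-reduction guidelines without a section number. The Grade 4 rows of Tables 4, 5, 7 and 9 (acneiform rash) say to discontinue.

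**The concern.** The same patient receives two instructions. Take a non-hematologic event that starts as intolerable Grade 2, is managed at 200 mg BID, and then reaches Grade 4. The bullet written for worsening on this pathway allows a hold and a restart, while two general rules and the event's own table require treatment to end. Grade 4 in Tables 4 and 5 means "Life-threatening consequences; urgent intervention indicated", and Table 7 gives hypertensive crisis among its Grade 4 examples. If a site followed the bullet, a patient could be re-exposed after an event of that kind. The stake is patient safety and uniform handling across sites. The two-stage design, its sample sizes and its error rates do not depend on this rule.

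**Working it through.** No arithmetic is involved beyond counting, and the plan gives no figure to reproduce. The check sets the rules side by side.

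**Step 1: what the bullet covers.** The trigger is ≥ Grade 3 with no upper bound. Section 6.1.1.2 has no sentence on Grade 4 and does not refer to 6.1.1.1. Read literally, Grade 4 is inside the trigger.

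**Step 2: one patient, each rule in turn.** A related non-hematologic event goes from intolerable Grade 2, on 200 mg BID, to Grade 4.

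| Source | Instruction |
|---|---|
| 6.1.1.2, third bullet | Hold 2 weeks; optional restart at 200 mg BID after recovery to Grade 1 or lower within 3 weeks |
| 6.1.1.1 | Discontinue |
| 6.1.3 | Discontinue |
| Grade 4 row of Table 4 (vomiting), 5 (diarrhea), 7 (hypertension) or 9 (acneiform rash) | Discontinue |

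The first row cannot be followed together with the others.

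**Step 3: which events are sent to 6.1.1.2.** Tables 2, 3, 4, 5, 7 and 9 lead there from Grade 2. Their event types are fatigue, nausea, vomiting, diarrhea, hypertension, acneiform rash and maculopapular rash: 1 + 1 + 1 + 1 + 1 + 2 = 7. Four of the 7 have a Grade 4 row that says to discontinue. The other 3 have no Grade 4 definition in their tables: fatigue and nausea have no such row, and maculopapular rash is marked as not applicable. For these routed events, 2 general rules + 4 table rows = 6 statements require the stop, against 1 bullet that allows a restart. Tables 6, 8, 10 and 11 also stop treatment at Grade 4, but they do not send Grade 2 events to 6.1.1.2 and are not counted.

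**Step 4: does the worst-grade sentence resolve it?** It points toward the stop, but it sits in 6.1.1.1 and speaks of decreasing the dose. Section 6.1.1.2 repeats the two reassessment sentences that come just before it in 6.1.1.1, leaves this one out, and supplies its own worsening rule in the third bullet. A site could reasonably take that bullet as the specific rule for this pathway.

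**Step 5: limits.** Both general stops concern non-hematologic toxicity. Hematologic events have their own rule in 6.1.2. The laboratory exception in 6.1.1.1 is separate and is not in question here.

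**The case against.** The strongest reply is that nobody reading the whole of Section 6.1 would restart after Grade 4. Section 6.1.1 introduces 6.1.1.1 and 6.1.1.2 together as guidance for Grades 2, 3 and 4. The stop in 6.1.3 covers any Grade 4 non-hematologic toxicity and makes no exception for events that began at Grade 2. The bullet only permits a restart, under conditions, and a permission does not normally override a categorical stop. In the four tables that define Grade 4 for a routed event, the stop stands two rows below the pointer to the Grade 2 guidelines. The QTc rule in 6.1.3 also starts from ≥ Grade 3 and says "Once QTc interval prolongation has resolved, orteronel may be restarted at the reduced dose level", and the Grade 4 stop follows it directly. That suggests the authors use ≥ Grade 3 loosely, subject to that stop.

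Most of this stands. It shows what was intended and that a site would have to overlook several statements to go wrong. It does not make the bullet correct. The QTc rule has the stop right after it, while 6.1.1.2 has neither a stop nor a cross-reference, and Section 6.1.1 does not say which of its two subsections prevails.

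A reader might also infer that the second bullet of 6.1.1.2, which allows a restart at 200 mg BID after an event still intolerable on that dose, breaks the rule in Section 6.1 that a patient who cannot tolerate the lowest dose must stop. The documents do not support calling that an error. Section 6.1 itself allows holds, so its stop can be read as applying once a hold and restart have failed. Writing such an exception into 6.1 would be a clinical choice for the sponsor.

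**Conclusion.** The third bullet of 6.1.1.2 is wrong as written for Grade 4 non-hematologic toxicity. It permits what 6.1.1.1, 6.1.3 and four table rows rule out. The practical risk is low because the intended rule is clear elsewhere, and the restart is optional and conditional. The documents give no event rates, so the count of statements in conflict describes the wording and does not estimate how many patients would be affected.

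Two stronger inferences are not supported. One is that the protocol as a whole endorses re-treatment after life-threatening events; six statements bearing on the routed events say the opposite. The other is that the bullet's Grade 3 part is equally in error. Section 6.1.1.1 itself allows a Grade 3 event to be held and then restarted at a reduced dose. Its stop, "If the Grade 3 toxicity recurs on the reduced orteronel dose, the drug should be discontinued", concerns recurrence, and an event that first reaches Grade 3 on 200 mg BID need not be one.

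The conclusion assumes that the Grade 2 guidelines named in Tables 3 to 5 are those of 6.1.1.2. The reduced dose is taken from Sections 5.1 and 6.1.1.2, because the milligram values in Table 1 are not readable in the text reviewed.

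**What to change.** In the third bullet of Section 6.1.1.2, delete the ≥ sign so that the trigger is Grade 3 only. Directly after the bullet, add "Grade 4 non-hematologic toxicity: Discontinue orteronel" with a reference to Section 6.1.1.1. Leave the exception for asymptomatic laboratory findings in 6.1.1.1 as it stands, and leave Section 6.1 unchanged.

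The cost is one symbol removed and one line added in a protocol amendment. No new data, visits or patients are needed.
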